5.3. Lifestyle Considerations

Throughout the study, participants may undergo medical assessments and review of compliance with requirements before continuing in the study.

5.3.1. Meals and Dietary Restrictions

Standard meals will be provided at all times while participants are resident at the CRU.

5.3.2. Substance Use: Caffeine, Alcohol, and Tobacco

- Participants should avoid caffeinated beverages while at the CRU, and for 12 hours prior to admission to the CRU. At other times during the outpatient period, participants are permitted to maintain their regular caffeine consumption. Decaffeinated beverages are permitted.
- Alcohol consumption is not permitted while at the CRU, and for 48 hours prior to admission and outpatient visits until leaving the CRU. At other times, participants are permitted to have an average weekly alcohol intake not exceeding 21 units per week (males \leq 65 years old) and 14 units per week (females). One unit is equal to:
 - 12 oz or 360 mL of beer,
 - 5 oz or 150 mL of wine, or
 - 1.5 oz or 45 mL of distilled spirits.
- Participants who smoke will be advised to not smoke more than 10 cigarettes per day during the study. Participants will be asked to refrain from smoking for approximately one hour prior to each ECG and vital sign measurement, and to abide by the CRU smoking restrictions.

5.3.3. Activity

- Participants will be advised to maintain their regular levels of physical activity or exercise during the study but to refrain from vigorous exercise.
- Strenuous activity should be avoided from 24 hours prior to admission until discharge from the CRU.
- While certain study procedures are in progress at the CRU, participants may be required to remain recumbent or sitting.

5.4. Screen Failures

A screen failure occurs when a participant who consents to participate in the clinical study is not subsequently randomly assigned to study intervention/enrolled in the study.

Individuals who do not meet the criteria for participation in this study (screen failure) may not be rescreened.

5.5. Criteria for Temporarily Delaying Enrollment/Randomization/Administration of Study Intervention of a Participant

Not applicable.

6. Study Intervention(s) and Concomitant Therapy

Study intervention is defined as any investigational intervention(s), marketed product(s), placebo, or medical device(s) intended to be administered to/used by a study participant according to the study protocol.

6.1. Study Intervention(s) Administered

CCI

6.1.1. Administration Details

CCI

6.1.1.1. Premedication for Infusions

CCI

1. **What is the primary purpose of the proposed legislation?**

2. **Who are the key stakeholders involved in the development of the proposed legislation?**

3. **What are the main provisions of the proposed legislation?**

4. **What is the timeline for the proposed legislation?**

5. **What are the potential impacts of the proposed legislation on the industry?**

6. **What is the proposed budget for the implementation of the legislation?**

7. **What is the proposed timeline for the implementation of the legislation?**

[figure not shown]
[figure not shown]
[figure not shown]
8. **What is the proposed budget for the ongoing monitoring and evaluation of the legislation?**

9. **What is the proposed timeline for the review and revision of the legislation?**

10. **What is the proposed budget for the review and revision of the legislation?**

6.1.1.2. Management of Infusion Reactions

CCI
CCI

6.2. Preparation, Handling, Storage, and Accountability

1. The investigator or designee must confirm appropriate storage conditions have been maintained during transit for all study intervention received and any discrepancies are reported and resolved before use of the study intervention.
2. Only participants enrolled in the study may receive study intervention. Only authorized study personnel may supply, prepare, or administer study intervention. All study intervention must be stored in a secure, environmentally controlled, and monitored (manual or automated) area in accordance with the labeled storage conditions with access limited to the investigator and authorized study personnel.
3. The investigator or authorized study personnel are responsible for study intervention accountability, reconciliation, and record maintenance (that is, receipt, reconciliation, and final disposition records).
4. Further guidance and information for the final disposition of unused study interventions are provided in the Study Reference Manual.

Note: In some cases, CRU may destroy the material if, during the CRU selection, the evaluator has verified and documented that the CRU has appropriate facilities and written procedures to dispose of clinical materials.

6.3. Measures to Minimize Bias: Randomization and Blinding

This is a participant- and investigator-blind study. The sponsor and site monitors are not blinded.

On Day 1, participants will be assigned a unique number (randomization number) in ascending numerical order. The randomization number encodes the participant's assignment to one of the 2 arms of the study (randomization ratio 5:1), according to the randomization schedule generated prior to the study by the statistics department at sponsor/designee. Each participant will be dispensed a blinded study intervention, labeled with the participant's unique randomization number, throughout the study.

Investigators will remain blinded to each participant's assigned study intervention throughout the course of the study. To maintain this blind, an otherwise uninvolved third party will be responsible for the reconstitution and dispensation of all study interventions and will endeavor to ensure that there are no differences in time taken to dispense following randomization.

In the event of a Quality Assurance audit, the auditors will be allowed access to unblinded study intervention records at the sites to verify that randomization or dispensing has been done accurately.

To preserve the blinding of the study, a minimum number of Lilly personnel and staff at the CRU (namely, CRU pharmacy staff) will see the randomization table before the study is complete. Individuals involved in study drug preparation will not be involved in any of the clinical aspects of the study, including study drug administration and AE assessments.

Blinding will be maintained throughout the conduct of the study as described in the blinding and unblinding plan section of the statistical analysis plan (SAP) or in a separate document.

Emergency codes will be available to the investigator. A code, which reveals the study intervention for a specific study participant, may be opened during the study only if the participant's well-being requires knowledge of the participant's treatment assignment.

If a participant's study treatment assignment is unblinded, the participant must be discontinued from the study, unless the investigator obtains specific approval from a Lilly clinical pharmacologist or CRP for the study participant to continue in the study. If a participant is discontinued, safety assessments will be collected per protocol for the remainder of the inpatient period. See early discontinuation procedures provided in SoA (Section 1.3). During the study, emergency unblinding should occur only by accessing the study participant's emergency code.

In case of an emergency, the investigator has the sole responsibility for determining if unblinding of a participant's treatment assignment is warranted for medical management of the event. The participant's safety must always be the first consideration in making such a determination. Where feasible and when timing of the emergent situation permits, the investigator should attempt to contact the Lilly medical monitor before unblinding a participant's treatment assignment. If the investigator decides that unblinding is warranted, it is the responsibility of the investigator to promptly document the decision and rationale and notify Lilly as soon as possible.

Upon completion of the study, all codes must be returned to Lilly or its designee.

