4.1.3. Follow-up Period

After discharge from CRU, participants will be required to visit the CRU on an outpatient basis at the timepoints indicated in SoA (Section 1.3). The follow-up period will be 12 weeks \pm 7 days after completion of dosing or until early discontinuation.

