7.1. Discontinuation of Study Intervention

Not applicable since this is single dose study.

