7.2. Participant Discontinuation/Withdrawal from the Study

Discontinuation is expected to be uncommon.

A participant may withdraw from the study:

- at any time at the participant's own request,
- at the request of the participant's designee (for example, parents or legal guardian),
- at the discretion of the investigator for safety, behavioral, compliance, or administrative reasons,
- if enrolled in any other clinical study involving an investigational product, or enrolled in any other type of medical research judged not to be scientifically or medically compatible with this study, and
- if the participant, for any reason, requires treatment with a therapeutic agent that is prohibited by the protocol and has been demonstrated to be effective for treatment of the study indication. In this case, discontinuation from the study occurs prior to introduction of the new agent.

At the time of discontinuing from the study, if possible, the participant will complete procedures for an early discontinuation visit and post-treatment follow-up as shown in the SoA. If the participant has not already discontinued the study intervention, the participant will be permanently discontinued from the study intervention at the time of the decision to discontinue the study.

If the participant withdraws consent for disclosure of future information, the sponsor may retain and continue to use any data collected before such a withdrawal of consent. If a participant withdraws from the study, the participant may request the destruction of any samples taken and not tested, and the investigator must document this in the site study records.

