8.2.4. Clinical Safety Laboratory Tests

- See Appendix 2 (Section 10.2) for the list of clinical laboratory tests to be performed and the SoA for the timing and frequency.
- The investigator must review the laboratory results, document this review, and report any clinically relevant changes occurring during the study as an AE. The laboratory results must be retained with source documents unless a Source Document Agreement or comparable document cites an electronic location that accommodates the expected retention duration. Clinically significant abnormal laboratory findings are those which are not associated with the underlying disease, unless judged by the investigator to be more severe than expected for the participant's condition.
- All laboratory tests with values considered clinically significantly abnormal during participation in the study or within the follow-up period after the last dose of study intervention should be repeated until the values return to normal or baseline or are no longer considered clinically significant by the investigator or medical monitor.
 - If such values do not return to normal/baseline within a period of time judged reasonable by the investigator, the etiology should be identified, and the sponsor notified.
 - All protocol-required laboratory assessments, as defined in Appendix 2, must be conducted in accordance with the SoA, standard collection requirements, and laboratory manual.
- If laboratory values from non-protocol specified laboratory assessments performed at an investigator-designated local laboratory require a change in participant management or are considered clinically significant by the investigator (for example, SAE or AE or dose modification), then report the information as an AE.

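### Protocol 6.3 makes leaving the study the default after unblinding; in a single-dose trial this can end scheduled safety follow-up without stopping any treatment

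*Protocol*

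**What the plan says.** Protocol 6.3 reserves the emergency code for cases in which a participant's "well-being requires knowledge of the participant's treatment assignment". Once an assignment is unblinded, "the participant must be discontinued from the study, unless the investigator obtains specific approval from a Lilly clinical pharmacologist or CRP" for continuation. For a participant who is discontinued, "safety assessments will be collected per protocol for the remainder of the inpatient period", and the section then refers to the early discontinuation (ED) procedures in the Schedule of Activities (SoA). It does not mention the outpatient visits.

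Four other places bear on what happens next:

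- Protocol 4.1.3 sets follow-up at 12 weeks ± 7 days "after completion of dosing or until early discontinuation". The synopsis and SAP Section 5 say the same.
- The SoA (Protocol 1.3) has one final column shared by Day 85 and ED, and nothing after it.
- Protocol 7.2 says that at discontinuation, if possible, "the participant will complete procedures for an early discontinuation visit and post-treatment follow-up as shown in the SoA".
- Protocol 8.3.1 closes AE collection when study participation ends.

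On stopping study intervention, Protocol 7.1 reads "Not applicable since this is single dose study". SAP Section 6 refers emergency unblinding back to the protocol.

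**The concern.** A rule that removes unblinded participants is easier to understand when treatment is still to come. Here a single dose is given on Day 1. A code break after dosing leaves nothing to stop except observation.

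Emergency code breaks are tied to the participant's well-being, so the person whose follow-up is cut short probably has a safety problem. The lost data are therefore plausibly informative for the primary endpoint, the incidence of TEAEs and SAEs. New non-serious events after the ED visit would go unrecorded. Late anti-drug antibody (ADA) samples would be lost, and for donanemab participants late PK samples too. Replacing the participant, which Protocol 9.5 allows, restores the group size but not that person's data.

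**Working it through.** **Reading the sections together.** Protocol 6.3 keeps inpatient safety assessments and points to the ED procedures. Protocol 4.1.3 ends follow-up at ED. The SoA gives ED one column, shared with Day 85. The most natural joint reading is that one ED visit replaces whatever outpatient schedule remains. Protocol 7.2 adds post-treatment follow-up to the ED visit and refers to the SoA for it. The SoA shows no schedule after ED; the only follow-up it shows is Day 8 to Day 85. So 7.2 can be read as keeping that schedule, or as adding nothing. The AE window in 8.3.1 depends on which reading sets the end of participation.

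**The plan's own counts.** 3 cohorts × 12 = 36. At 5:1, each cohort has 12 × 5/6 = 10 on donanemab and 2 on placebo, so 30 and 6 in total. This agrees with Protocol 9.5.

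**Scheduled after dosing (SoA).**

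- Outpatient visits: Days 8, 15, 22, 29, 43, 57, 71, 85 = 8.
- PK: end of infusion, 3, 24, 48, 72 and 96 h = 6, plus 8 outpatient = 14.
- ADA: Days 15, 29, 57, 85 = 4.
- Laboratory panels: Days 2, 5, 15, 29, 85 = 5.

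As a check against the blood sampling table (Protocol 10.2.1): laboratory panels 5 + Day -1 = 6 and ADA 4 + predose = 5 both agree. For PK, the SoA gives 14 + predose = 15, while the table shows 14 (+3). The SoA count is used here.

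**Loss for one participant.** Net loss = items scheduled after the last visit attended − 1 for the ED visit.

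| Last visit attended | Visits lost | PK lost | ADA lost | Lab panels lost |
|---|---|---|---|---|
| Day 5 | 8 − 1 = 7 | 8 − 1 = 7 | 4 − 1 = 3 | 3 − 1 = 2 |
| Day 15 | 6 − 1 = 5 | 6 − 1 = 5 | 3 − 1 = 2 | 2 − 1 = 1 |
| Day 29 | 4 − 1 = 3 | 4 − 1 = 3 | 2 − 1 = 1 | 1 − 1 = 0 |
| Day 57 | 2 − 1 = 1 | 2 − 1 = 1 | 1 − 1 = 0 | 1 − 1 = 0 |

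These figures assume that the ED visit takes place and that inpatient PK samples are kept. Neither is guaranteed: 7.2 asks for the ED visit only if possible, and 6.3 keeps safety assessments without naming PK. With no ED visit, the Day 5 row becomes 8 visits, 8 PK, 4 ADA and 3 panels. At the other end, the loss is zero if continuation is approved or if 7.2 is read as full follow-up. The PK column matters only for donanemab, because Protocol 8.4.1 plans no assay of placebo samples.

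**Weight of one participant.** 1/10 = 10% of a donanemab dose group; 1/6 = 17% of pooled placebo.

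**Frequency (assumption).** The documents give no code-break rate. For illustration, take p = 0.1% to 2% per participant.

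- Expected code breaks: 36p = 0.04 to 0.72.
- Chance of at least one: 1 − (1 − p)^36 = 3.5% to 52%. This is the chance of a code break, not of lost data; sponsor approval and the alternative reading of 7.2 are not factored in.
- Share of the 36 × 8 = 288 outpatient visits lost if every break left Day 5 as the last visit and each ED visit took place: p × 7/8 = 0.09% to 1.75%.

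**The case against.** The strongest reply is that the passages hardly conflict. Sections 6.3, 4.1.3, 7.2 and the SoA all fit one plain reading, in which a single ED visit closes follow-up. The alternative rests on one phrase in 7.2, qualified by feasibility. Much of this stands. A reader might infer a flat contradiction, but the documents support only an undefined phrase that can be read another way. The plain reading, however, is the one that loses the data.

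A second reply is that discontinuation is not automatic. That is correct. The sponsor may approve continuation, and because it is already unblinded (Protocol 6.3, SAP Section 6) it can do so without further harm to the blind. No criteria for approval are given, so the default still decides unless someone acts.

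Third, the main safety information is protected. Protocol 8.3 keeps follow-up of events that are serious, related or the cause of discontinuation. Under 8.2.4, clinically significant abnormal laboratory tests "should be repeated until the values return to normal or baseline or are no longer considered clinically significant". Section 8.3.1 keeps SAEs judged possibly related reportable after participation ends. The participant stays in the Safety population, and if a TEAE prompted the break, the percentage with any TEAE does not change. What remains exposed is later new non-serious events and scheduled samples.

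Fourth, Protocol 6.3 allows the unblinding plan to sit in a separate document, which was not available. It might settle the question in practice, though the protocol wording would still need to agree with it.

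**Conclusion.** The point holds as a low-priority, inexpensive improvement. After dosing, the default in 6.3 ends observation only, and on the most natural reading it cuts the outpatient schedule to one ED visit. With Day 5 as the last visit and the ED visit completed, 7 of 8 outpatient visits are lost. Expected impact on the trial is small. Protocol 7.2 expects discontinuation to be uncommon, no hypothesis is tested, and the safeguards above cover the most serious events.

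Three stronger readings go too far. The lost data are not certainly informative: the emergency code is tied to well-being, but the discontinuation rule covers any unblinding, which could include accidental disclosure. The 7-of-8 figure is not a maximum, since a missed ED visit or missing inpatient PK would add to it. Nothing is claimed about a break during the infusion, because the administration sections are redacted. The result rests on the joint reading of 6.3, 4.1.3 and the shared Day 85/ED column; the frequency figures rest on an assumed code-break rate.

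**What to change.** Reconcile Protocol 6.3, 7.2, 4.1.3, the synopsis, the Day 85/ED column of the SoA and SAP Section 5 so that unblinding by itself does not end data collection already scheduled to Day 85 (AEs, laboratory tests, ADA, PK). This would remain subject to consent and to the withdrawal grounds already in 7.2. Define the post-treatment follow-up that applies after an ED visit, or delete the phrase. In the SAP, flag unblinded participants and identify their post-unblinding data in listings and summaries.

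The cost is wording plus a flag: the sample size does not change, and the visits are already in the schedule. The downside is that later AE severity and causality ratings for that participant are not blind, which is why the flag is needed. The change concerns data collection only and leaves clinical management as it is.

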6.4. Study Intervention Compliance

Study intervention will be administered under medical supervision by designated CRU staff. The dose of study intervention and study participant identification will be confirmed prior to the time of dosing. The date and time of the dose administered will be recorded in the source documents and will be provided to the sponsor as requested.

6.5. Dose Modification

This is a parallel treatment, single dose study. Dose adjustments are not permitted in this study.

6.6. Continued Access to Study Intervention after the End of the Study

Not applicable.

6.7. Treatment of Overdose

For this study, any dose of study intervention greater than dose of study intervention assigned through randomization will be considered an overdose.

In the event of an overdose, the investigator or treating physician should:

- Contact the medical monitor immediately.
- Closely monitor the participant for any AE/serious adverse event (SAE) and laboratory abnormalities.
- Obtain a plasma sample for PK analysis if requested by the medical monitor (determined on a case-by-case basis).

6.8. Concomitant Therapy

Any medication or vaccine, including over-the-counter or prescription medicines, vitamins, and/or herbal supplements, that the participant is receiving at the time of enrollment or receives during the study must be recorded along with:

- Reason for use.
- Dates of administration including start and end dates.
- Dosage information including dose and frequency for concomitant therapy of special interest.

The medical monitor should be contacted if there are any questions regarding concomitant or prior therapy.

Participants must abstain from taking prescription or nonprescription drugs (including vitamins and dietary or herbal supplements) within 14 days or five half-lives (whichever is longer) before the start of study intervention until completion of the follow-up visit, unless, in the opinion of the investigator and sponsor, the medication will not interfere with the study.

Acetaminophen, at doses of \leq 2 grams/day, is permitted for use in a 24-hour period at the discretion of the investigator. Other concomitant medication may be considered on a case-by-case basis by the investigator in consultation with the medical monitor if required.

7. Discontinuation of Study Intervention and Participant Discontinuation/Withdrawal

Discontinuation of specific sites or of the study as a whole are handled as part of Appendix 1 (Section 10.1).

7.1. Discontinuation of Study Intervention

Not applicable since this is single dose study.

7.2. Participant Discontinuation/Withdrawal from the Study

Discontinuation is expected to be uncommon.

A participant may withdraw from the study:

- at any time at the participant's own request,
- at the request of the participant's designee (for example, parents or legal guardian),
- at the discretion of the investigator for safety, behavioral, compliance, or administrative reasons,
- if enrolled in any other clinical study involving an investigational product, or enrolled in any other type of medical research judged not to be scientifically or medically compatible with this study, and
- if the participant, for any reason, requires treatment with a therapeutic agent that is prohibited by the protocol and has been demonstrated to be effective for treatment of the study indication. In this case, discontinuation from the study occurs prior to introduction of the new agent.

At the time of discontinuing from the study, if possible, the participant will complete procedures for an early discontinuation visit and post-treatment follow-up as shown in the SoA. If the participant has not already discontinued the study intervention, the participant will be permanently discontinued from the study intervention at the time of the decision to discontinue the study.

If the participant withdraws consent for disclosure of future information, the sponsor may retain and continue to use any data collected before such a withdrawal of consent. If a participant withdraws from the study, the participant may request the destruction of any samples taken and not tested, and the investigator must document this in the site study records.

